	# Responses (inclusive)
3	Never stop with this many patients
6	0
9	0-1
12	0-2
15	0-3
18	0-4
21	Always stop with this many patients

Stopping boundaries for toxicity

# Patients (in complete cohorts of 3) (inclusive)	Stop the trial if there are this many toxicities total:
	# Toxicities (inclusive)
3	Never stop with this many patients
6	4-6
9	5-9
12	7-12
15	8-15
18	10-18
21	Always stop with this many patients

Summary of operating characteristics

The operating characteristics are summarized in the table below. The probabilities of stopping the trial early are exact calculations from MultcLean Desktop under the assumption that response is independent of toxicity.

True Toxicity Rate	True OR Rate	Prob(stop the trial early)	Avg # patients enrolled (25 th – 75 th percentile)
0.2	0.6	0.04	20.5 (21 – 21)
	0.5	0.07	20.1 (21 – 21)
	0.4	0.19	19.0 (21 – 21)
	0.3	0.45	16.4 (12 – 21)
0.3	0.6	0.14	19.2 (21 – 21)
	0.5	0.17	18.8 (21 – 21)
	0.4	0.28	17.8 (15 – 21)
	0.3	0.51	15.5 (9 – 21)
0.4	0.6	0.36	16.4 (9 – 21)
	0.5	0.39	16.2 (9 – 21)
	0.4	0.46	15.4 (9 – 21)
	0.3	0.63	13.6 (6 – 21)
0.5	0.6	0.64	12.9 (6 – 21)
	0.5	0.66	12.7 (6 – 15)
	0.4	0.70	12.2 (6 – 21)
	0.3	0.79	11.1 (6 – 15)

Analysis Plan

Summary statistics will be provided for continuous variables. Frequency tables will be used to summarize categorical variables. Logistic regression will be utilized to assess the effect of patient prognostic factors on the response rate and the toxicity rate. The distribution of time-to-event endpoints will be estimated using the method of Kaplan and Meier. Cox proportional hazard regression will be employed for multivariate analysis on time-to-event outcomes.

An Efficacy/Safety Summary will be submitted to the IND Office Medical Monitor, after the first 6 evaluable patients complete 8 weeks of study treatment, and every 3 evaluable patients thereafter. Toxicity information of previously submitted patients will be updated during every submission.

Trial Conduct

Conducting a trial designed by this method does not require software since the stopping conditions have been tabulated before the trial begins.

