4.0 TREATMENT PLAN

This is a single arm, open label, phase II study of ibrutinib, nivolumab and blinatumomab in patients with RT.

[figure not shown]

Figure 4. Schematic of treatment plan

Patients will receive treatment as follows:

1. 2 cycles of 3 drug combination (ibrutinib, nivolumab and blinatumomab). These cycles will be 8 weeks each.
2. 9 cycles of 2 drug combination (ibrutinib and nivolumab). These cycles will be 4 weeks each.
3. Maintenance treatment with ibrutinib monotherapy until disease progression following completion of nivolumab.

4.1 Ibrutinib therapy.

Ibrutinib treatment will commence on cycle 1, day 1 at 420mg/d. Dose reductions to 280mg/d or 140mg/d are allowed per treating physician discretion, but the reason must be documented in the medical record. Ibrutinib will be given continuously until disease progression or toxicity.

4.2 Nivolumab therapy.

Patients will receive nivolumab for up to a total of 52 weeks. Dosing will be 240mg IV every 2 weeks, commencing on day 1 until 2nd response assessment, then 480mg IV every 4 weeks.

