The existing trial of blinatumomab as a single agent assumes that a toxicity rate greater than 31% would be excessive. Since we propose combining blinatumomab with two additional agents, we aim to achieve a higher ORR, and allow for acceptable toxicity no higher than 40%. For the purposes of toxicity monitoring, toxicity will be defined as follows: grade 4-5 neurotoxicity or CRS; grade 3 neurotoxicity or CRS that fails to resolve within 1 week or recurs at grade ≥ 3 severity on re-challenge; grade 3-5 therapy-related immune-related toxicity at least possibly related to nivolumab.

For the Bayesian design, the following parameter settings will be used:

- For the standard treatment response and toxicity rates, constant rates of 0.4 are assumed.
- For the response and toxicity rates under the proposed treatment, a beta(0.8, 1.2) prior is assumed for each rate, which has the same mean as the rates under the standard treatment, and an effective sample size of 2.
- The maximum number of patients if no early stopping is applied will be 21, and a minimum of 6 patients will be treated before stopping.
- The planned cohort size is 3.

- The trial will be stopped early based on response if the posterior probability that the response rate of the experimental treatment is less than the current standard rate is greater than 0.9.
- The trial will be stopped early based on toxicity if the posterior probability that the toxicity rate of the experimental treatment is greater than the current standard rate is greater than 0.8.
- Toxicity will be monitored continuously for the first year of treatment.

Response Stopping Boundaries

# Patients (in complete cohorts of 3) (inclusive)	Stop the trial if there are this many responses total:

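### The toxicity criterion has no count at 21 patients, so the complete one-year toxicity data are never compared with it

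*Combined protocol and SAP*

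**What the plan says.** All references are to the combined protocol and SAP.

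- **Limit.** Section 14.0 says the plan will "allow for acceptable toxicity no higher than 40" percent.
- **Criterion.** "For the standard treatment response and toxicity rates, constant rates of 0.4 are assumed", and "a beta(0.8, 1.2) prior is assumed for each rate". Early stopping for toxicity is triggered when the posterior probability that the experimental toxicity rate is "greater than the current standard rate is greater than 0.8". The matching response rule uses "less than the current standard rate is greater than 0.9".
- **Window.** "Toxicity will be monitored continuously for the first year of treatment". The monitored events include grade 3-5 immune-related toxicity at least possibly related to nivolumab. Section 4.2 adds: "Patients will receive nivolumab for up to a total of 52 weeks".
- **Table.** The toxicity boundaries are 4, 5, 7, 8 and 10 events at 6, 9, 12, 15 and 18 patients. The entry at 21 is "Always stop with this many patients", and the response table closes with the same words.
- **Conduct.** Under Analysis Plan, summaries go to the IND Office Medical Monitor once the first 6 evaluable patients have completed 8 weeks, and then for every 3 more. Toxicity in patients already submitted is brought up to date each time. Under Trial Conduct, the trial is run from the tabulated conditions, without software.

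**The concern.** Row 21 answers one question: does enrolment continue? The toxicity table also carries the plan's only numerical test of its 40% limit, and the toxicity window runs well past enrolment. Three sets of data have no tabulated count to be compared with: events in patients 19 to 21, late events in everyone after the 18-patient look, and the final total.

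At stake is a safety conclusion. The trial could end with a toxicity count that the plan's own prior and cutoff would flag, while the report correctly says that no boundary was crossed. Some patients may still be on nivolumab when the count gets there. The Analysis Plan offers frequency tables and a logistic regression for the toxicity rate, but no final posterior or interval against 40%.

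**Working it through.** **Inputs** (section 14.0): prior Beta(0.8, 1.2); reference rate 0.4; toxicity cutoff 0.8; response cutoff 0.9; cohorts of 3; first look at 6 patients; maximum 21; response independent of toxicity.

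**Formula.** With k toxicities in n patients, the posterior is Beta(0.8 + k, 1.2 + n − k). The boundary is the smallest k with P(rate > 0.4) > 0.8.

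**1. Reproduce the printed boundaries, then continue to 21.**

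| n | one below boundary | at boundary | printed |
|---|---|---|---|
| 6 | 3: 0.657 | 4: 0.875 | 4 |
| 9 | 4: 0.585 | 5: 0.8005 | 5 |
| 12 | 6: 0.736 | 7: 0.882 | 7 |
| 15 | 7: 0.681 | 8: 0.834 | 8 |
| 18 | 9: 0.788 | 10: 0.896 | 10 |
| 21 | 10: 0.745 | 11: 0.861 | none |

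The five response boundaries also reproduce. The plan's own settings therefore imply 11-21 for row 21.

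**2. Reproduce the operating characteristics.** Exact enumeration of cumulative toxicity and response counts, with looks at 6 to 18 and none at 21, matches all 16 printed early-stopping probabilities within 0.01 and the average sample sizes within 0.1. For example, at toxicity 0.5 and response 0.6 the calculation gives 0.643 and 12.87, against 0.64 and 12.9 printed.

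**3. Highest count that passes unflagged, if events are known at each look.** 9 of 18 does not stop the trial (0.788 < 0.8). Three more events in the last cohort give 12/21 = 57%, with posterior 0.935.

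**4. How often the gap matters, if events are known at each look** (true response rate 0.6).

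| true toxicity | stops early | reaches 21 with 11 or more | share of trials reaching 21 | criterion met at any look, row 21 added |
|---|---|---|---|---|
| 0.3 | 0.143 | 0.004 | 0.4% | 0.147 |
| 0.4 | 0.362 | 0.020 | 3% | 0.382 |
| 0.5 | 0.643 | 0.040 | 11% | 0.683 |

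At 0.5, for instance, 1 − 0.643 = 0.357 of trials reach 21, and 0.040 / 0.357 = 0.11. The last column is early stopping (either rule) plus the row-21 cases: 0.643 + 0.040 = 0.683. Exactly 12/21 has probability about 0.7% at 0.5 and 0.2% at 0.4.

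**5. Late onset (assumption; the documents give no split).**

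- *Without updating.* Suppose a fraction f of toxicities is visible at the looks and the rest appear only after the last one. The looks then see rate p·f, and each remaining patient later has an event with probability p(1 − f)/(1 − p·f). With f = 0.75 or 0.5, the chance of reaching 21 with 11 or more is 0.10 or 0.16 at p = 0.4, and 0.27 or 0.44 at p = 0.5. These are upper-end figures, because earlier patients are in fact updated at later looks.
- *With updating.* If accrual pauses for each 8-week look and 25-50% of toxicities arise in weeks 16 to 52, simulation gives about 5-10% at 0.4 and 9-26% at 0.5.

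**6. What 11 or 12 of 21 would establish.** The 90% credible intervals are 0.344-0.681 at 11/21 and 0.387-0.721 at 12/21. Both include 0.40.

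**The case against.** The strongest case on the other side is that nothing is broken. The rule is about stopping early, and at 21 there is nobody left to enrol. The response table ends the same way, and the published operating characteristics reproduce without a look at 21. This stands: row 21 is not a misprint, and a count there could not affect accrual.

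Four stronger readings are tempting, and the documents do not support them.

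- *The toxicity rule is never really applied.* It is applied five times, with earlier patients' data refreshed at each submission.
- *Nobody reviews safety after enrolment.* Read literally, the three-patient schedule includes a Medical Monitor summary at 21. Sections 11.2, 11.3 and 11.5 keep serious-event reporting going, with capture to 100 days after the last dose. What is missing is a number to judge the total against.
- *A large share of trials would end unflagged.* From the documents alone the share is 2.0% at 0.4 and 4.0% at 0.5. Sections 5.1.2.3 and 5.1.2.7 give early median onset for blinatumomab events (2 days for cytokine release, 9 days for neurologic events), and these are two of the three toxicity components. Section 5.2.5.5 says endocrine events on nivolumab may appear after many months, but gives no frequency.
- *Eleven of 21 would show toxicity above 40%, or a row-21 count would keep the observed rate below it.* The interval at 11/21 includes 0.40, and 10/21 (48%) would still pass. That tolerance comes from the 0.8 cutoff, not from row 21.

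It is also fair to say that 40% is a monitoring parameter and that safety is a secondary endpoint. That makes the final posterior a reporting improvement. It does not explain why a year of monitoring should have no criterion once the last look has passed.

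**Conclusion.** The point holds as a limited gap. The criterion is used at 6 to 18 patients, but the complete 21-patient, one-year toxicity data are never compared with it, and the plan is run from the table alone. Results of 11 or 12 of 21 (52% or 57%; posterior 0.861 or 0.935), or more with late events, can occur with no tabulated boundary met.

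The size is small if toxicities are known at each look: 2.0% of all trials at true toxicity 0.4 and 4.0% at 0.5, or 11% of trials that reach 21 at 0.5. These figures assume a true response rate of 0.6 and independence of response and toxicity, as in the plan's own calculations. The gap widens with late onset, but every larger figure in step 5 depends on onset and accrual assumptions that the documents do not supply. It is worth correcting because the remedy uses only settings already in the plan and costs almost nothing.

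**What to change.** In section 14.0:

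1. State that row 21 ends enrolment, and add a toxicity count of 11-21 to that row. This is the count implied by the stated prior and the 0.8 cutoff.
2. Assess it at the 21-patient summary, and keep it live until the last patient completes the first year of treatment.
3. If it is reached, notify the IND Office Medical Monitor and report that the plan's toxicity criterion was met. Do not report that toxicity has been shown to exceed 40%.
4. In the Analysis Plan, add the final posterior probability that toxicity exceeds 0.40, with its 90% credible interval.

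This sets no dosing or treatment rule. The cost is one table entry, a few sentences and possibly a less favourable safety statement. The published early-stopping probabilities and average sample sizes stay as they are, because all 21 patients are already enrolled when the new entry applies.

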3.0 STUDY POPULATION

30 patients will be enrolled in this phase II study, 9 in the blinatumomab monotherapy phase and 21 in the combination phase.

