14.0. STATISTICAL CONSIDERATIONS

The cohort of 9 patients already treated demonstrates the feasibility and safety of blinatumomab as a single agent for the treatment of RT. The overall toxicity profile of blinatumomab in RT was very favorable and this cohort of patients can be used as a “safety cohort,” prior to proceeding with a phase II study evaluating the combination with ibrutinib + nivolumab. As discussed above, the combination of ibrutinib and nivolumab was also very well tolerated.

We have completed a phase II study of ibrutinib + nivolumab, and achieved an ORR of 43%. This will serve as our “base case” estimation of the response rate that we would see with the combination of ibrutinib + nivolumab. If blinatumomab (ORR 1/8 = 12.5%) provides additive benefit only, this will result in an ORR of 50-55% with the combination of ibrutinib + nivolumab and blinatumomab. However, we expect synergy between the two regimens. We have therefore designed our statistical analysis around achieving an ORR of approximately 60%, which would suggest some synergy

between the two regimens. Higher response rates would suggest a greater degree of synergy between blinatumomab and ibrutinib + nivolumab, which we hope to achieve.

We propose to enroll an additional 21 patients, with the goal of evaluating the efficacy and safety of the proposed combination therapy. A sample size of 21 patients ensures that, if the trial is not terminated early, a posterior 90% credibility interval for overall response rate will have width of 0.33, under the assumption of a 60% of overall response rate (13/21 responses) and beta prior as described below. Under this scenario, the lower boundary of the 90% credibility interval matches the 43% ORR that was seen with ibrutinib + nivolumab therapy.

The primary outcome will be overall response (ORR), assessed after completion of 2 courses of blinatumomab.

We will utilize a Bayesian trial design to enable simultaneous monitoring of efficacy and toxicity using the approach of Thall, Simon, and Estey (1995, 1996). After an initial 6 patient safety cohort, subsequent patients will be enrolled in cohorts of size 3.

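### Multivariable Cox and ordinary logistic regression of prognostic factors are planned on at most 21 patients, where estimates are unstable and exaggerated; single-factor, penalised or exact estimates suit the data better

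*Combined protocol and SAP*

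**What the plan says.** The Analysis Plan in Section 14.0 contains two regression statements. For binary outcomes: "Logistic regression will be utilized to assess the effect of patient prognostic factors on the response rate and the toxicity rate". For time-to-event outcomes: "Cox proportional hazard regression will be employed for multivariate analysis on time-to-event outcomes". Only the Cox statement calls for a multivariable model.

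On size, Section 14.0 says "The maximum number of patients if no early stopping is applied will be 21" and "a minimum of 6 patients will be treated before stopping". Section 3.0 gives the wider count: "30 patients will be enrolled in this phase II study, 9 in the blinatumomab monotherapy phase and 21 in the combination phase". The 9 earlier patients had a different treatment, and nothing says that they enter these models.

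The plan does not name the covariates, limit their number or give a selection rule. It sets no significance level, multiplicity rule or method for sparse data, and does not label the regressions exploratory. The 21 patients are justified only by the precision of the response rate.

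**The concern.** A multivariable model needs enough events, or enough patients in the smaller outcome class, to separate the effects of its covariates. Here there are few of either, while candidate factors are plentiful. Section 2.1 discusses TP53 disruption, clonal relationship and two clinical prognostic models. Table 3 collects a FISH panel, cytogenetics, a sequencing panel, IGHV status and CD38. A model with three to five covariates would comply with the text.

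At stake is the credibility of any prognostic factor reported from the trial: very large or infinite odds ratios, and hazard ratios well above the truth whenever they reach significance.

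**Working it through.** **The plan's own precision figure.** At 13/21 responses and a beta(0.8, 1.2) prior, the posterior is beta(13.8, 9.2). Its 5th and 95th percentiles are 0.430 and 0.760, a width of 0.329. The plan states a width of 0.33 and a lower bound matching 43%, so this reproduces. It concerns one proportion and says nothing about regression.

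**Outcomes available at 21 patients.**
- Non-responders at the planning result: 21 − 13 = 8.
- Toxicities: 21 × 0.2 = 4.2 to 21 × 0.4 = 8.4. The lower rate is the smallest in the operating-characteristics table; the upper is the plan's ceiling for acceptable toxicity.
- Progression or death events: not stated. I assume 50-90% of patients, or 10-19 events, given the historical median survival below one year in Section 2.1 and surveillance to two years in Table 4.

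**One covariate, by hand** (assumed binary, 50% prevalence, two-sided 5%).
- Cox, 15 events: the 95% interval is the estimate times or divided by exp(1.96/√(15 × 0.25)) = 2.75. An estimate below about 2.75 is therefore not significant, so a true hazard ratio of 2 can reach significance only when overestimated.
- Hazard ratio detectable with 80% power: exp((1.96 + 0.84)/√3.75) = 4.25. Over 10-21 events it runs from 5.9 to 3.4.
- Events needed for hazard ratio 2 at 80% power: 4 × (1.96 + 0.84)²/(ln 2)² ≈ 66, about three times the maximum number of patients.
- Logistic, 20% toxicity: the chance that one factor level has no toxicities, so that the odds ratio is zero or infinite, is 2 × 0.9²¹ − 0.8²¹ = 0.219 − 0.009 = 0.21. Simulation gave about 22%.
- Logistic, 60% response: the chance of an empty cell is about 2 × 0.8²¹ + 2 × 0.7²¹ = 0.018 + 0.001 = 0.02.

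**Two to five covariates, by simulation** (n = 21, independent binary covariates at 50% prevalence, two-sided 5%; 3,000 runs per Wald setting, 1,500 per likelihood-ratio setting).

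| Model | Median estimate | Near-separation | Rejection per null coefficient | At least one false positive |
|---|---|---|---|---|
| Cox, 10-19 events | True HR 2: 2.06-2.38; 4.2-10.1 among significant results | – | Wald 4.4-9.2%, LR 5.9-10.6% | Wald 7-34%, LR 11-38% |
| Logistic, 40-60% event rate | True OR 3: 3.5-5.1 | 4-27% | Wald 0.2-2.7%, LR 6.5-13.8% (all event rates) | Wald 1-8.5%, LR 13-44% (all event rates) |
| Logistic, 20% toxicity | True OR 3: 4.0-6.4 | 31-64% | as above | as above |

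LR is the likelihood-ratio test. With one covariate, Cox type I error is 3.8-5.9%. If the trial stopped at 12 patients with 50% events, the 2-5 covariate Cox model gave divergent or extreme estimates in 14-50% of runs.

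**Effect of the change.** In a separate simulation at n = 21, 60% response and five null covariates, multivariable maximum likelihood separated in about 24% of runs. It rejected 12% per covariate by likelihood ratio, and 39% of null odds ratios were more than 4-fold from 1. Single-factor Firth estimation gave 4% and 14%. The comparison changes two things at once, the number of covariates and the penalisation, so it does not apportion the gain.

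**The case against.** The strongest case on the other side has five parts.

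1. A reader might infer that the logistic models are also multivariable. The text does not say so, and one-factor fits would already comply. This stands. The remaining logistic point is that ordinary, unpenalised fitting is fragile, especially for toxicity, where even one factor fails about a fifth of the time.
2. A reader might infer that these regressions generally produce too many false positives. They do not: one-covariate Cox is near nominal, two covariates add little, and logistic Wald tests are conservative. The excess appears with likelihood-ratio tests or with about three or more Cox covariates. This stands.
3. Much of the chance of any false positive is plain multiplicity. Independent 5% tests give 1 − 0.95³ = 14% for three factors and 1 − 0.95⁵ = 23% for five. Testing one factor at a time does not remove that. This stands, and it is why the remedy needs a short list and an open label.
4. A reader might take these as the trial's only prognostic results. Sections 1.0 and 13.1 plan exploratory immunologic and microRNA analyses against response, so that is not supported.
5. Stopping at 6 patients is the extreme case. At 60% response and 20% toxicity the plan's table gives a 0.04 chance of early stopping and 20.5 patients on average. At 40% toxicity these become 0.36 and 16.4, so smaller samples are possible but need not be the premise.

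None of this answers the instability and exaggeration at the full 21 patients.

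**Conclusion.** The point holds as a low-cost improvement. A multivariable Cox model and ordinary logistic regression are poor choices for 21 patients with about 8 non-responders and 4-8 toxicities. The firm conclusion is instability and exaggeration, increasing with the number of covariates. A general claim of inflated false-positive rates is not supported.

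The simulated rates are conditional. The documents give no number of covariates, prevalence, significance level or test, and the event fraction and the true effects (HR 2, OR 3) are also assumptions.

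The consequence is limited. No primary or secondary endpoint in Section 1.0 is a prognostic-factor analysis, and neither the primary response estimate nor the stopping rules use these models.

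**What to change.** Reword the Analysis Plan as follows.

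- Drop the multivariable Cox model.
- Name a short list of factors in advance, for example TP53 disruption, which Section 2.1 already identifies as prognostic, and analyse them one at a time.
- For response and toxicity, use Firth-penalised or exact logistic estimates.
- For progression-free and overall survival, show Kaplan-Meier curves by group, with a single-covariate Cox hazard ratio and interval if wanted. Kaplan-Meier estimation is already planned in general terms.
- Report estimates with intervals rather than significance. Single-factor analysis alone does not cure overestimation among results selected for being significant.
- Label the results hypothesis-generating and state that multiplicity is not controlled.

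The cost is a few sentences. The loss is mutually adjusted estimates, which 21 patients cannot support. Even after the change these analyses remain descriptive: with 15 events, only a hazard ratio of about 4.25 would be detectable with 80% power.
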